7.3.2. Endpoints

The study will identify non-fatal and fatal events of the following types:

- Primary endpoints:
 - Endometrial cancer;
 - Endometrial hyperplasia.
- Secondary endpoints:
 - Venous thromboembolism;
 - Coronary heart disease (defined as myocardial infarction [MI] and sudden death);
 - Stroke (including transient ischemic attack [TIA]);
 - Breast cancer;

- Ovarian cancer;
- Thyroid cancer;
- Renal cancer and adenoma;
- Gastrointestinal cancer;
- Any cancer (any malignant neoplasm);
- All-cause mortality.

All endpoints are included in the EU risk management plan (RMP) for CE/BZA (*Duavive*). Estrogen-associated cancers (breast, ovarian, endometrial cancers) and endometrial hyperplasia are important potential risks in the RMP based on the medical literature for HRT and background incidence rates (IRs) in postmenopausal women. An important identified risk potentially associated with *Duavee* use is VTE because it is a known safety concern for both of the individual component products of CE/BA (i.e., CE and BZA monotherapies). According to the literature,⁶ MI and stroke are important potential risks that are associated with the use of HRT products in general. Thyroid cancer, renal cancer, renal adenoma, and gastrointestinal tract cancers are considered as important potential risks based on their elevated background incidence in postmenopausal women. All cancers are included because of their inclusion in the EU RMP for CE/BZA. All-cause mortality is included to provide context to fatal occurrences of the safety endpoints. For example, if a finding of increased fatal stroke events is observed, it could be assessed if this result coincided with an increase in all-cause mortality.

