
Hypertension
	
401.xx-405.xx, 437.2x, V81.1x
	
CPT: 3077F, 3080F

Breast Pain
	
611.71
	

Diabetes
	
250.xx (Type 1: 250.x1, 250.x3; Type 2: 250.x0, 250.x2)
	

Renal Disease	403.01, 403.11, 403.91, 404.02, 404.03, 404.12, 404.13, 404.92, 404.93, 582.xx, 583.0x-583.7x, 585.xx, 586.xx, 588.0x, V42.0x, V45.1x, V56.xx	
Osteoarthritis	715.xx	
Osteoporosis	733.0x, V82.81	
Major Depression	296.2x, 296.3x, 311.xx, V79.0x	HCPCS: G8959, G8960, G8126, G8127, G9193-G9195, CPT: 3088F-3093F
History of VTE/CVA/CHD Event	415.1x, 451.11, 451.19, 451.2x, 451.81, 453.8, 414.xx, 430.xx-438.xx, V12.51-V12.54	
History of Breast, Ovarian, or Endometrial Malignancy	174.xx, 198.81, V10.3x, 198.6x, 183.0x, 236.2x, 182.0x, 198.82, V10.43, V10.42	19120, 58950-58954, 58956-58958, 58960

Family history of cancer	V16.xx	
Hysterectomy	V88.01, V88.02	ICD-9-CM procedure: 68.4x-68.7x CPT: 58150-58294

Potential Algorithms for Claims-Based Identification of Safety Endpoints*

Event	Algorithm
Endometrial Cancer	To be determined via validation
Endometrial Hyperplasia	To be determined via validation
Venous Thromboembolism	Hospitalization with any of the following ICD-9-CM diagnosis codes listed as the principal discharge diagnosis: 415.1x, 451.11, 451.19, 451.2x, 451.81, 453.8x
CHD (i.e. MI, fatal MI, and Sudden Death)	MI defined as a hospitalization with ICD-9-CM code 410.xx (excluding 410.x2) with either (1) a length of stay between 3 and 180 days or (2) discharge status indicating death if length of stay is less than 3 days.
Stroke/TIAs	Hospitalization with ICD-9-CM diagnosis codes 433.x1, 434.x1, 436.x, 437.x1, 437.9x with either (1) a length of stay between 3 and 180 days or (2) death if length of stay is less than 3 days, or hospitalization with a principal discharge diagnosis of 435.xx (TIA)
Breast Cancer	At least two outpatient or one inpatient ICD-9-CM diagnosis code(s) 174.xx.
Ovarian Cancer	At least two outpatient or one inpatient ICD-9-CM diagnosis code(s) 183.0x.

Thyroid Cancer	Thyroidectomy during follow-up and ≥ 2 ICD-9-CM 193.xx diagnosis codes recorded.
Renal Cancer	At least two outpatient or one inpatient ICD-9-CM diagnosis code(s) 189.x
Renal adenoma	At least two outpatient or one inpatient ICD-9-CM diagnosis code(s) 223.x
Gastrointestinal Tract Cancer	At least two outpatient or one inpatient ICD-9-CM diagnosis code(s) 150.x – 159.x

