All Cancers (Malignancies)	At least two outpatient or one inpatient ICD-9-CM diagnosis code(s) in the following range: 140.xx-208.xx

*Endpoints will be identified in the NDI based on the presence of applicable codes listed as cause of death.

Algorithms for Claims-Based Identification of Safety Endpoints Identified in the Literature

Event type	Algorithm	Study Population	Validation
CHD (MI, fatal MI and sudden death)	MI defined as a hospitalization with ICD-9-CM code 410.xx (excluding 410.x2) with either (1) a length of stay between 3 and 180 days or (2) death if length of stay is less than 3 days.	HIRD patients receiving COX-2 inhibitors	In HealthCore data, this had a PPV of 88.4% (83.2% - 92.5%), which was higher in patients receiving COX2-inhibitors (92.3 versus 84.2%). Previously reported PPV of 94% in Medicare data.

CHD (MI, fatal MI and sudden death)
	
At least one occurrence of any of the following codes: ICD-9 diagnosis codes: 410 - 414, 433 - 438, 440 - 441, 4439. ICD-9 procedure codes: 3601 - 3609, 361, 362, 3812, 3813, 3818, 3925, 3926, 3929, 3950, 3990 CPT codes: 33510 - 33545, 33572, 34101 - 34111, 34201 - 34203, 35301, 35311 - 35381, 35390, 35454 - 35456, 35459, 35470, 35473 - 35474, 35482 - 35483, 35485, 35492 - 35493, 35495, 35533, 35541 - 35571, 35641, 35646, 35654, 92975, 92980 - 92984, 92995 - 92996
 
*Note - this includes codes for angina, MI, CABG and other procedures not included in the study definition.
	
HIRD patients receiving statins
	
Sensitivity of 96%, specificity of 93% and Kappa of 0.82 (PPV not calculated).

Stroke/TIA
	
An algorithm using primary discharge diagnosis codes for acute ischemic or hemorrhagic stroke (International Classification of Diseases, Ninth Revision, Clinical Modification codes: 430, 431, 433.x1, 434.x1, 436).
	
Medicare patients
	
Positive predictive value of 92.6% (95% confidence interval, 88.8%-96.4%), a specificity of 99.8% (99.6%-99.9%), and a sensitivity of 59.5% (53.8%-65.1%). An algorithm using only acute ischemic stroke codes (433.x1, 434.x1, 436) had a positive predictive value of 91.1% (95% confidence interval, 86.6%-95.5%), a specificity of 99.8% (99.7%-99.9%), and a sensitivity of 58.6% (52.4%-64.7%).

[figure not shown]

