Stroke/TIA	Diagnosis codes for acute ischemic or hemorrhagic stroke (International Classification of Diseases, Ninth Revision, Clinical Modification codes: 430, 431, 433.x1, 434.x1, 436) in any position	Medicare data linked to Women's Health Initiative patients	Specificity was 99.7%, negative predictive value was 99.7%, sensitivity was 82.8%, positive predictive value was 85.8%, and $\kappa=0.84$. Whereas specificity and negative predictive value exceeded 99%, sensitivity ranged from 75% to 88% and positive predictive value ranged from 80% to 90% across stroke definitions.
Stroke/TIA	
Ischemic stroke without TIA: (1) Hospitalization with ICD-9-CM diagnosis codes 433.x1, 434.x1, 436.x, 437.x1, 437.9x with either (1) a length of stay between 3 and 180 days or (2) death if length of stay is less than 3 days.
 
(2) Hospitalization with ICD-9-CM diagnosis codes 433.x1, 434.x1 with either (1) a length of stay between 3 and 180 days or (2) death if length of stay is less than 3 days.
	HIRD patients receiving COX-2 inhibitors	
In HealthCore data, algorithm 1 had a PPV of 87.4%, and algorithm 2 95.5% based on review of 175 cases
 
A prior study of Medicare beneficiaries saw a PPV of 96% for algorithm 1.

Breast cancer	
At least one inpatient diagnostic or procedure code for breast cancer: Malignant neoplasm of female breast: 174.0-174.9 Any Incisional breast biopsy: 85.12 Excision or destruction of breast tissue: 85.20 - 85.25 Subcutaneous mastectomy: 85.33-85.36 Mastectomy: 85.41-85.48
	Piedmont cancer registry	The sensitivity of the algorithm was 76.7%, positive predictive value 87.9%.

Breast cancer	At least one claim with ICD-9-CM code 174.xx, 233.0, 238.3 or 239.3.	HealthCore	Not formally validated, however in this study 766 medical records were reviewed to stage breast cancer. Internal communication was that medical records were not excluded based on lack of evidence of breast cancer. 13.4% of cases were stage zero, and 10.3% could not be staged.

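### The only stroke algorithm given is an ischemic stroke list plus TIA, so non-fatal hemorrhagic stroke would go uncounted in an endpoint called stroke

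*Protocol*

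**What the plan says.** Section 7.3.2 lists the secondary endpoint as "Stroke (including transient ischemic attack [TIA"]), with no subtype limit. The reason given there is equally general: "MI and stroke are important potential risks that are associated with the use of HRT products in general".

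Appendix 2, in the table of potential algorithms, gives one stroke definition for the study. Its stroke part is a hospital stay coded "433.x1, 434.x1, 436.x, 437.x1, 437.9x" that lasts 3 to 180 days, or ends in death if shorter. Its TIA part is "or hospitalization with a principal discharge diagnosis of 435.xx (TIA").

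The literature table in the same appendix describes several published stroke algorithms. One, validated in the HIRD, reads "Ischemic stroke without TIA: (1) Hospitalization with ICD-9-CM diagnosis codes 433.x1, 434.x1, 436.x, 437.x1, 437.9x" and carries the same length-of-stay and death rule. Another, from Medicare data, is introduced as "An algorithm using primary discharge diagnosis codes for acute ischemic or hemorrhagic stroke" and lists 430 and 431 beside 433.x1, 434.x1 and 436.

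Appendix 2 calls its lists candidates. Final definitions are to follow further literature review, in preparation for the first annual report.

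**The concern.** The endpoint's name and its code list cover different things. A hospital stay coded only 430 or 431 would not be counted in claims, yet the result would be reported as stroke to a regulator that has stroke in its risk management plan as an important potential risk.

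No later step in the protocol would show the gap. Section 7.7.1 says that secondary endpoints are not validated in this project and that their rates get no PPV correction. Section 7.9 counts the high HIRD PPV for stroke as a strength, but the HIRD stroke validation tabulated in Appendix 2 concerns ischemic stroke only.

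**Working it through.** **Comparison of code lists (Protocol, Appendix 2)**

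| Source | Codes | Protocol's description |
|---|---|---|
| Study algorithm, stroke part | 433.x1, 434.x1, 436.x, 437.x1, 437.9x | Stroke/TIA |
| Study algorithm, TIA part | 435.xx | TIA |
| Literature, HIRD, algorithm 1 | 433.x1, 434.x1, 436.x, 437.x1, 437.9x | Ischemic, without TIA |
| Literature, Medicare (two entries) | 430, 431, 433.x1, 434.x1, 436 | Ischemic or hemorrhagic |
| Literature, Medicare, reduced set | 433.x1, 434.x1, 436 | Ischemic only |

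1. The stroke part of the study algorithm is identical to HIRD algorithm 1, in codes and in length-of-stay rule.
2. The fourth row minus the fifth leaves {430, 431}. By the protocol's own contrast, these are the hemorrhagic codes.
3. The study list contains neither. No section states or justifies the omission.

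**Size**

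The protocol gives no stroke rate, no hemorrhagic share and no TIA share, so there is no stated figure to reproduce and the loss can only be shown under assumptions.

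Let h be the hemorrhagic share of strokes and t the TIA share of all endpoint events. The share of endpoint events lost is f = h × (1 − t). If the standard error of the log HR varies as 1/√(events) and both cohorts lose the same share, the interval widens by 1/√(1 − f).

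| h (assumed) | t (assumed) | f | 1/√(1 − f) |
|---|---|---|---|
| 0.10 | 0.30 | 0.10 × 0.70 = 0.07 | 1/√0.93 = 1.04 |
| 0.20 | 0.30 | 0.20 × 0.70 = 0.14 | 1/√0.86 = 1.08 |
| 0.10 | 0 | 0.10 | 1/√0.90 = 1.05 |
| 0.20 | 0 | 0.20 | 1/√0.80 = 1.12 |

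The first two rows apply to the endpoint as defined, with TIA in it. The last two apply to stroke without TIA.

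The two sensitivities quoted for the Medicare algorithm (59.5% with 430 and 431, 58.6% for ischemic codes only) do not measure this loss. The protocol does not say that both were taken against the same set of true strokes.

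**The case against.** **The list is provisional.** This is true: the table is headed as potential algorithms, and final definitions are deferred. A reader might infer that the ischemic list is already the fixed endpoint definition, and the protocol does not support that. But it is the only study definition given. The literature already tabulated contains 430 and 431, and nothing signals that they will be added.

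**The choice has a visible rationale.** Among the stroke entries in Appendix 2, only the one holding the ischemic lists was validated in the HIRD, with a PPV of 87.4% for the list used here. The lists with 430 and 431 come from Medicare data, use a primary-diagnosis or any-position rule, and carry no length-of-stay rule. This stands as a reason to keep the ischemic list as a component. It does not justify calling the result stroke.

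**Fatal cases may be found through the NDI.** A reader might infer that hemorrhagic stroke can never count as an outcome. That is too strong. Appendix 2 says that NDI endpoints rest on the applicable cause-of-death codes without naming them, so fatal hemorrhagic stroke might be captured. If it is, the composite would hold all fatal strokes but only ischemic non-fatal ones.

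**The covariates do not settle what was intended.** The history covariate for prior VTE, CVA or CHD events spans 430.xx-438.xx, from which a reader might infer that hemorrhagic codes were meant as outcomes too. But that row is broader than the outcomes elsewhere: it includes 414.xx, while the CHD outcome uses 410.xx. The CVD covariate, which names stroke, omits 430 and 431.

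**An effect on hemorrhagic stroke would be undetectable anyway.** This largely stands. Ten months for each of 5,400 projected Duavee users gives 5,400 × 10/12 = 4,500 person-years by the third report. At an assumed 10-30 hemorrhagic strokes per 100,000 person-years, 0.45 to 1.35 events are expected. Follow-up continues after discontinuation, so person-time may be longer, but doubling it gives only 0.9 to 2.7. The loss of such a signal cannot be charged mainly to the code list. What can be charged to it is the mislabelled result.

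**Conclusion.** The point holds as a mismatch between a secondary endpoint and its only given code list. As written, the plan would count ischemic stroke and TIA, miss non-fatal hemorrhagic stroke and report the result as stroke, without justifying the restriction.

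Total stroke incidence would be understated. The amount cannot be computed from the protocol. With a 10-20% hemorrhagic share and TIA at 30% of events, both assumed, about 7-14% of endpoint events are lost and the interval is about 4-8% wider on the log scale. The mismatch itself does not depend on those assumptions.

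A reader might also infer that the HR is biased. The protocol does not show this: incomplete capture that is equal in the two cohorts, with similar HRs by subtype, need not shift the HR. If the subtypes differed, the HR would describe ischemic stroke and TIA only. The defect should be corrected because the repair is cheap and the definitions are still open. It does not touch the primary endpoints.

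**What to change.** When definitions are finalised before the first interim report:

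- Add 430 and 431 to the stroke algorithm, and state the diagnosis position and length-of-stay rule that apply to them.
- Apply the same definition of stroke to NDI causes of death, naming the codes.
- Keep the HIRD-validated ischemic list as a separately reported component.

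This costs a code-list edit and one more line of results. The small downside is that the enlarged algorithm is validated nowhere in the protocol: the 87.4% HIRD PPV would cover only the ischemic component, and the report should say so.

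Alternatively, rename the endpoint ischemic stroke/TIA throughout, justify the restriction, and limit the conclusions to that endpoint. This is a text edit that leaves the validated list unchanged, but the study then says nothing about non-fatal hemorrhagic stroke.

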7.3.2.2. Secondary Endpoints

Secondary study endpoints include VTE, CHD, stroke, breast cancer, ovarian cancer, thyroid cancer, renal cancer, renal adenoma, gastrointestinal tract cancers, all cancers, and all-cause mortality. The major cardiovascular endpoints are well studied in database research, with multiple validation studies in databases, including the HIRD. In addition, certain cancer

[figure not shown]
endpoints also have been studied. Based on a targeted literature search to identify automated database studies of the endpoints of interest with a focus on validation studies in claims databases, we have identified validated algorithms for the identification of VTE, CHD, stroke, breast cancer and thyroid cancer, which are described in Appendix 3. For secondary endpoints where validated algorithms were not identified, ie, renal cancer, renal adenoma, gastrointestinal cancer and all cancers, algorithms using diagnostic codes have been developed, as shown in Appendix 3.

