Thyroid cancer	Various, see validation	Optum database	PPV of 53.1% (95% CI 42.8 – 63.1) for the ICD-9 code 193 alone. Additionally requiring a thyroidectomy identified 50 of 52 cases but also captured 16 non-cases (PPV 75.8%; 95% CI 63.4-85.1). Requiring a primary inpatient visit with the ICD9 code removed 41 of the 46 non-cases but only identified 16 of the cases (PPV 76.2%; 95% CI 52.5-90.9). One algorithm yielded a PPV of 91.5% (95% CI 78.7-97.2%). This algorithm required cases to have a thyroidectomy during follow-up and ≥ 2 ICD9 193 codes ≤ 90 days of this event, identifying 43 cases and 4 non-cases.
Venous thromboembolism	Multiple	Mini-Sentinel evidence review, various algorithms identified.	The highest PPV (65%-95%) was reported for the combined use of ICD-9 codes 415 (pulmonary embolism), 451, and 453 (deep vein thrombosis) as a VTE event.

*Review of the literature is ongoing; final definitions will be selected using the most current literature and coding available at the start of analyses.

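### The candidate thyroid cancer rule omits the 90-day condition of the version with a documented PPV of 91.5%, so its own PPV is undocumented; the breast cancer rule also matches no validated version

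*Protocol*

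**What the plan says.** Section 7.3.2.2 of the protocol sorts the secondary endpoints by how they will be identified. For one group it says "we have identified validated algorithms for the identification of VTE, CHD, stroke, breast cancer and thyroid cancer". For renal cancer, renal adenoma, gastrointestinal cancer and all cancers, no validated algorithm was found and rules based on diagnosis codes were written instead.

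In Appendix 2, the table of potential endpoint algorithms opens the thyroid cancer rule with "Thyroidectomy during follow-up" and gives it in full as "Thyroidectomy during follow-up and ≥ 2 ICD-9-CM 193.xx diagnosis codes recorded".

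The literature table later in Appendix 2 describes several thyroid variants tested in the Optum database. For the best of them it reports "One algorithm yielded a PPV of 91.5% (95% CI 78.7-97.2%)" and adds: "This algorithm required cases to have a thyroidectomy during follow-up and ≥ 2 ICD9 193 codes ≤ 90 days of this event", with the counts given as "identifying 43 cases and 4 non-cases". A looser variant, code 193 plus thyroidectomy, "identified 50 of 52 cases but also captured 16 non-cases (PPV 75.8%; 95% CI 63.4-85.1)".

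For breast cancer, the planned rule is one inpatient or two outpatient 174.xx codes. The literature table has two breast entries. One uses inpatient diagnosis or procedure codes. The other uses a single claim from a wider code set and is described there as not formally validated.

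Section 7.7.1 states that only the primary endpoints are validated within this study and that incidence rates for secondary endpoints will not be corrected for PPV.

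**The concern.** The planned thyroid rule is worded almost exactly like the 91.5% version, but the time link between the surgery and the codes is gone. A thyroidectomy and two 193.xx codes recorded far apart during follow-up, which can last up to four years, would count as a case. Elsewhere the protocol does carry time conditions across: the planned myocardial infarction rule keeps the 3-to-180-day length of stay of its published source. The omission for thyroid cancer is not flagged or explained.

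Because secondary endpoints are not validated in this study, the literature figures are the only support for how accurately thyroid and breast cancer are identified. If the rule used is not the rule that was validated, that support does not carry over. Additional false positives would pull the hazard ratio towards 1, which in a safety study is the direction that hides a risk.

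**Working it through.** **Inputs** (all from the thyroid entry of the Appendix 2 literature table)

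- Code 193 alone: PPV 53.1%. The counts that follow from the entry are 52 cases and 46 non-cases.
- Code 193 plus thyroidectomy: 50 cases, 16 non-cases.
- Thyroidectomy plus at least two 193 codes within 90 days: 43 cases, 4 non-cases.

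**Step 1. Reproduce the stated figures.** PPV = cases / (cases + non-cases).

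- 90-day rule: 43/47 = 91.5%. The Wilson interval with continuity correction is 78.7% to 97.2%, as stated.
- Code plus thyroidectomy: 50/66 = 75.8%. The same method gives 63.4% to 85.1%, as stated.

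**Step 2. Place the planned rule.** It requires a thyroidectomy and at least two codes, with no window. Every woman flagged by the 90-day rule is also flagged by the planned rule, and every woman flagged by the planned rule is also flagged by code plus thyroidectomy. This takes 193 and 193.xx as the same codes and assumes no unstated time limit in the looser variant. The planned rule would therefore have found 43 to 50 cases and 4 to 16 non-cases in that sample.

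- Lowest PPV: 43/(43 + 16) = 43/59 = 72.9%.
- Highest PPV: 50/(50 + 4) = 50/54 = 92.6%.

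The upper bound is slightly above 91.5%. The table does not separate the effect of the second code from that of the window, so the range cannot be narrowed.

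**Step 3. Translate to the hazard ratio.** Suppose false positives occur at the same rate in both cohorts, sensitivity is equal in both, and PPV refers to the E+P cohort. For a true hazard ratio of 2.0,

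observed HR = 2 × PPV + (1 − PPV) = 1 + PPV.

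| Rule | PPV | Observed HR |
|---|---|---|
| 90-day rule | 43/47 | 1.91 (1.9149) |
| Planned rule, lowest | 43/59 | 1.73 |
| Planned rule, highest | 50/54 | 1.93 |

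**Step 4. Incidence.** Dividing by PPV does not give the error in the rate, because each rule also misses cases. Against 52 confirmed cases, the 90-day rule flags 47 (47/52 = 0.90) and code plus thyroidectomy flags 66 (66/52 = 1.27). The net error can go in either direction.

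**Step 5. Breast cancer, by comparison of text.** The planned rule has the same form as the renal and gastrointestinal rules, which Section 7.3.2.2 puts in the group without validated algorithms. It matches neither breast entry in the literature table.

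**The case against.** The strongest reply is that nothing is fixed yet. Appendix 2 calls its entries candidates, the table is headed as potential algorithms, and both the introduction and a footnote say that final definitions will be chosen after further literature review. That stands, and it makes this a small and easily corrected point. It does not remove it: Section 7.3.2.2 makes its statement about validated algorithms without that reservation, and an unflagged omission can pass into the final definition.

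Three further objections limit what may be concluded.

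- Section 7.3.2.2 quotes no PPV. A reader might infer that it claims 91.5% for the planned rule. It does not; that figure appears only in Appendix 2.
- A reader might infer that dropping the window lowers the PPV, perhaps to the 75.8% of the looser variant. That variant needs no second code, the planned rule does, and the bounds in Step 2 include values above 91.5%.
- A reader might blame the lack of PPV correction for a diluted hazard ratio. The correction in Section 7.7.4 multiplies case counts by the PPV to adjust an incidence rate. It would not change a hazard ratio even if it were extended to secondary endpoints.

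It is also fair to say that the protocol gives no thyroid cancer rate, so practical importance cannot be shown, and that Section 7.9 already acknowledges outcome misclassification in general.

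**Conclusion.** The mismatch is real but minor. As written, the thyroid rule is none of the variants with documented performance, and the breast rule is in the same position, although Section 7.3.2.2 groups both with validated endpoints. For thyroid cancer the supportable statement is that the PPV is undocumented and lies somewhere between 72.9% and 92.6% on the protocol's own counts. A true hazard ratio of 2.0 would then be seen as about 1.73 to 1.93.

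This rests on the nesting of the three rules, on false positives unrelated to exposure, and on the Optum counts carrying over to the HIRD. The last is an assumption even for the 90-day rule. The documents support neither a claim that accuracy is poor nor a statement that incidence is overstated by a given percentage.

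**What to change.** When the definitions are finalised:

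- In Appendix 2, add to the thyroid rule that the two codes must fall *within 90 days of the thyroidectomy*. Alternatively, keep the rule and label it a modified version that has not been validated.
- In Section 7.3.2.2, claim validation only for algorithms used as they were validated.
- Align the breast cancer rule with a validated version, or move breast cancer to the group with code-based rules.
- In the same edit, correct the pointer in Section 7.3.2.2, which sends the reader to Appendix 3 for algorithms that are in Appendix 2.

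The cost is a few words and no new data. The 90-day rule has a drawback: it found 43 of 52 cases (82.7%), whereas up to 50 of 52 (96.2%) might be found without the window. If the missed cases are spread equally over both cohorts, they cost precision but bias the hazard ratio less than false positives do. Restoring the window also does not give a PPV measured in the HIRD, and the text should say so.

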Similarly to the primary endpoints, the IR and multivariate adjusted HR will be calculated for the following *a priori* defined secondary safety endpoints: VTE, stroke, CHD, breast cancer, ovarian cancer, thyroid cancer, renal cancer, renal adenoma, gastrointestinal tract cancers, all cancers and all-cause mortality among study subjects initiating *Duavee* or E+P HRT. Because only the primary endpoints are being validated as part of this project, positive predictive value (PPV) correction of IR estimates for secondary endpoints will not be performed.

For all analyses, each endpoint will be identified first in the automated claims data (i.e., endpoints that were not fatal prior to the patient reaching the healthcare system) and then, for study reports that include NDI linkage, through either the automated data or the NDI (i.e., a composite of non-fatal and fatal endpoints, such as endometrial cancer and death due to endometrial cancer). Analyses that include NDI linkage will be restricted to the time period that is available in both the HIRD and NDI data sources (i.e., through the end of the 2016 calendar year if the first NDI search is performed in preparation for the Final Study Report).

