Appendix 2. Codes and Algorithms

Candidate codes and algorithms for identification of exposures, endpoints and covariates are provided below. Final definitions will be determined based on further review of the literature in preparation for development of the first Annual Interim Report, and updates may be provided in the event that additional codes become available during the course of the study (e.g., new GPI, ICD-9-CM, HCPCS or CPT codes become available, including introduction of ICD-10 in the US).

Cohort defining medications

Product	GPI Code
Duavee® (Conjugated estrogens/Bazedoxifene)	24995002100330
Activella® (containing Estradiol, Norethindrone)	2499300212x
Angeliq® (containing Drospirenone, Estradiol)	2499300240x
FemHRT® (containing Ethinyl Estradiol, Norethindrone)	2499300225x
Jinteli™ (containing Ethinyl Estradiol, Norethindrone)	2499300225x
Mimvey™ (containing Estradiol, Norethindrone)	2499300212x
Prefest® (containing Estradiol, Norgestimate)	2499300265x
Premphase® (containing Conjugated Estrogens, Medroxyprogesterone)	2499300204x
Prempro® (containing Conjugated Estrogens, Medroxyprogesterone)	2499300204x

Medications included as covariates

Classification	GPI code
Corticosteroids	22x
Lipid lowering agents	39x
Antihypertensives	36x
Antidepressants	58x
Anticonvulsants	72x
Sedatives/ hypnotics	60x
Antimycobacterial agents	90x

Macrolides	35x
Antifungal	11x
Antivirals	12x
Antidiabetics	27x, excluding 2730x and 2757x
Testosterone	23100030x
Local hormone treatments	2600003010x, 2600004000x, 2600004010x 5535001000x, 5535002000x, 5535002010x, 5535002500x, 5535003000x 5537006000x
History of oral contraceptive use	2510x
	2599x
History of intrauterine devise (IUD)	2505x
	2520x

Comorbidities

Description	Diagnosis and Procedure Codes	
	ICD-9-CM	Procedural
Vasomotor symptoms (VMS)	627.2x, 782.62	
Obesity	278.xx, V77.8x	
Polycystic ovarian syndrome (PCOS)	256.4x, 628.xx, 704.1x,	

CVD (i.e. stroke, transient ischemic attack, sudden cardiac death, myocardial infarction, peripheral vascular disease, coronary artery surgery (CABG), or congestive heart failure)
	
093.0x, 394.xx-397.xx, 398.91, 401.9x, 402.xx, 404.01, 404.03, 404.11, 404.13, 404.91, 404.93, 410.xx-414.xx, 424.xx, 425.4x-425.9x, 427.xx, 428.xx, 429.2x, 429.9x, 433.xx-435.xx, 437.3x, 440.xx, 441.xx, 443.1x-443.9x, 447.1x, 557.1x, 557.9x, 798.2x, 798.9x, V43.4x
	
ICD-9-CM procedure: 36.1x, 36.2x, CPT: 33510-33545 33572

Hyperlipidemia
	
272.0x-272.4x
	

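### The candidate renal cancer (189.x) and renal adenoma (223.x) algorithms take whole urinary-organ code categories and, if carried forward, would count non-renal lesions as renal events

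*Protocol*

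**What the plan says.** Protocol Section 7.3.2 lists "Renal cancer and adenoma" among the secondary endpoints and gives the reason for including them: "Thyroid cancer, renal cancer, renal adenoma, and gastrointestinal tract cancers are considered as important potential risks". Section 7.7.1 plans an incidence rate and an adjusted HR for each.

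Appendix 2 puts them into codes. Renal cancer is "At least two outpatient or one inpatient ICD-9-CM diagnosis code(s) 189.x" and renal adenoma is "At least two outpatient or one inpatient ICD-9-CM diagnosis code(s) 223.x". In the same table ovarian cancer is "At least two outpatient or one inpatient ICD-9-CM diagnosis code(s) 183.0x", and the MI rule takes 410.xx but leaves out 410.x2.

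On validation, Section 7.3.2.2 groups the two renal endpoints with those lacking a validated algorithm: "For secondary endpoints where validated algorithms were not identified, ie, renal cancer, renal adenoma, gastrointestinal cancer and all cancers". Section 7.7.1 adds that "positive predictive value (PPV) correction of IR estimates for secondary endpoints will not be performed".

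On status, Appendix 2 opens with "Candidate codes and algorithms for identification of exposures, endpoints and covariates are provided below". It defers the final definitions to the preparation of the first annual interim report and foresees updates, including for ICD-10. (Section 7.3.2.2 refers the reader to Appendix 3 for these algorithms; they are in Appendix 2.)

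**The concern.** The endpoints are named by organ, but the codes are not limited to that organ. The classification places kidney and renal pelvis at the fourth digits 0 and 1 of both categories. The remaining digits cover other urinary sites: ureter (189.2, 223.2), urethra (189.3, and within 223.8), bladder (223.3, benign), and other or unspecified urinary organs. An open fourth digit takes them all. This is a question of anatomical site, separate from the rule of two outpatient codes or one inpatient code.

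Both endpoints come from the EU risk management plan, and their rates and HRs will be read as statements about the kidney. Non-renal lesions would raise the rate reported as renal. If treatment does not affect them, they would also pull a real renal HR towards 1. Nothing planned downstream would separate the two kinds of lesion.

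**Working it through.** **Step 1: does the open digit take the whole category?** Set the rows of the Appendix 2 endpoint table side by side.

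| Endpoint | Code string | Narrowed below the category? |
|---|---|---|
| Ovarian cancer | 183.0x | Yes, fourth digit fixed |
| MI | 410.xx excluding 410.x2 | Yes, by exclusion |
| Renal cancer | 189.x | No |
| Renal adenoma | 223.x | No |

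In the table's own notation an x stands for any digit, and a limit is written out where one is meant. So 189.x and 223.x take every sub-code.

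**Step 2: are all the sub-codes renal?** The protocol prints no code labels. It does adopt ICD-9-CM as its coding language (Sections 7.3.4 and 7.4.1, Appendix 2), and that classification fixes the meaning of each sub-code. Both categories cover the kidney and other urinary organs. This step rests on the code listing, which is not in the protocol, and should be confirmed there.

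**Step 3: would a later step remove the non-renal codes?**
- Medical-record validation covers endometrial cancer and endometrial hyperplasia only (Section 7.3.2.1, Appendix 3).
- The PPV sensitivity analysis covers the primary endpoints only (Section 7.7.4), and Section 7.7.1 rules out PPV correction for secondary endpoints.
- NDI endpoints are taken from the applicable codes listed as cause of death (note to the Appendix 2 table), so the same scope could pass to fatal events.

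No planned step removes them.

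**Step 4: size.** There is no figure to reproduce. Table 1 projects precision for the endometrial endpoints only, and no renal count, rate or PPV is stated. What follows is illustration on an assumed input.

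Let s be the share of comparator-cohort qualifying events that are non-renal, and assume treatment does not affect those lesions. Scale the comparator's observed rate to 1. Its renal part is 1 − s. The *Duavee* rate is then HR × (1 − s) + s, so

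observed HR = 1 + (1 − s)(HR − 1).

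| s (assumed) | True HR 2.0 | True HR 1.5 |
|---|---|---|
| 0.10 | 1 + 0.9 × 1.0 = 1.90 | 1 + 0.9 × 0.5 = 1.45 |
| 0.30 | 1 + 0.7 × 1.0 = 1.70 | 1 + 0.7 × 0.5 = 1.35 |

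The comparator's renal rate would be overstated by 1/(1 − s) − 1, which is 11% at s = 0.10 and 43% at s = 0.30. At a true HR of 2.0 the overstatement in the *Duavee* cohort is smaller, s/[2(1 − s)]: 0.10/1.8 = 6% and 0.30/1.4 = 21%.

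**The case against.** The strongest reply is that nothing has yet been fixed. The lists are called candidate, the table is headed as potential algorithms, and a closing note says final definitions will follow the literature and coding current at the start of analyses. A reader might infer from the code strings that non-renal lesions are already being counted. The documents do not support that; they show only what would happen if the candidate codes were adopted unchanged. The reply does not dispose of the point, however. These are the only renal definitions given, the planned literature review has already found no validated renal algorithm, and no passage commits to checking anatomical site.

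A second reply is that the protocol nowhere states what the 189 and 223 sub-codes contain. That is true, and it is why the listing should be checked before the edit is made. But the meaning belongs to the coding system the protocol has chosen; it is not an outside study result.

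A third reply concerns consequence. A reader might infer that one benign bladder lesion could surface as a renal safety signal. The documents do not go that far. Section 7.7.6.2 requires at least one event in each cohort and at least four in total before any HR is estimated. One misclassified *Duavee* event could therefore complete the threshold only if the comparator cohort already had at least three. Section 7.7.7 describes the study as estimation rather than hypothesis testing, and the protocol sets no signal rule.

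**Conclusion.** The point holds as a matter for finalising the definitions. As written, the candidate algorithms are wider than the endpoints they are meant to capture, and no validation or PPV correction would remove the excess. The conclusion rests on the standard content of ICD-9-CM categories 189 and 223 and on the codes being carried forward unchanged.

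The size is unknown. The 10-30% share is an assumption with no source in the documents, applied alike to a malignant and a benign category whose true shares may differ. The observed HR of 1.9-1.7 for a true 2.0 shows the direction and form of the effect, not an estimate of it, and neither those figures nor the rate inflation should be cited as a finding about this study. The impact is confined to unvalidated secondary endpoints; the endometrial analyses are untouched.

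**What to change.** When the definitions are finalised before the first annual interim report:

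1. Confirm the sub-codes of 189 and 223 against the ICD-9-CM listing.
2. Restrict renal cancer to 189.0 and renal adenoma to 223.0. State explicitly whether renal pelvis (189.1, 223.1) is included.
3. Carry the same sites into the ICD-10 mapping and the NDI cause-of-death codes.
4. Leave the excluded malignant 189 sites in the any-cancer endpoint, whose range 140.xx-208.xx already contains them. Drop the excluded benign 223 sites or list them descriptively. They must not be moved into any cancer, which Section 7.3.2 and Appendix 2 limit to malignant neoplasms.

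The cost is a code-list edit with no change to design or data extraction. The downside is slightly fewer events for two endpoints that may already be sparse.
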